6.6.1.1. Management of Serious Infections

Participants should be closely monitored for the development of signs and symptoms of infection during and after treatment with study drug. Study drug should be interrupted if a participant develops a serious infection or a serious opportunistic infection. A participant who develops a new infection during treatment with study drug should undergo prompt diagnostic testing appropriate for an immunocompromised participant. As appropriate, antimicrobial therapy should be initiated, and the participant should be closely monitored. Study drug may be restarted once the infection has been successfully treated. Participants with new evidence of TB must be permanently discontinued from study drug.

6.6.1.2. Management of Herpes Zoster

If a participant develops herpes zoster, consider temporarily interrupting study drug until the episode resolves.

6.6.1.3. Management of COVID-19

Participants who develop symptoms of COVID-19 may continue treatment with study drug.

In cases where treatment of COVID-19 with nirmatrelvir/ritonavir (or another strong CYP3A4 inhibitor or strong/moderate inducer for COVID-19 treatment) is required, study drug must be interrupted for up to 7 days to allow the antiviral treatment course to complete. Study drug may be restarted after a minimum of 7 days after the last dose of the antiviral therapy.

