6.6.1. Criteria and Procedures for Dose Interruptions and Adjustments of Study Drug

Safety concerns should be discussed with the sponsor immediately upon occurrence or awareness to determine if the participant should continue or discontinue study drug.

Treatment with study drug may be interrupted for up to 28 days, unless otherwise specified in the Protocol or a longer period is approved by the sponsor (or designee), to allow for resolution of toxicity. The principal investigator (or designee) should contact the sponsor to discuss the case of any participant whose treatment has been interrupted for more than 21 days (but less than 28 days) before restarting treatment. Participants may resume treatment if no medical condition or other circumstance exists that, in the opinion of the investigator, would make the participant unsuitable for further participation in the study.

Guidelines for interruption, restarting, and discontinuation of study drug are outlined in [Table 8](#) as well as in [Appendix E](#) (for COVID-19) and Section 6.6.1.6 (for emergency and elective surgeries).

Table 8: Guidelines for Interruption, Restarting, and Discontinuation of Study Drug

Laboratory Value	Action Taken
Chemistry	
ALT and/or AST is $> 3.0 \times < 20$ ULN	
Step 1: Interrupt study drug.
 
Step 2: Confirm whether potential Hy's law criteria have been met (see Appendix D), following applicable procedures. If potential Hy's law criteria are not met, proceed to Step 3.
 
Step 3: Repeat ALT/AST assessments weekly for up to 3 weeks or until ALT and/or AST results are $< 3.0 \times$ ULN and then restart study drug at the same dose.
 
If ALT and/or AST result(s) do not decrease to $< 3.0 \times$ ULN after 3 weeks of drug interruption, study drug will be permanently discontinued, and the participant will follow EOT visit procedures; a post-treatment follow-up visit (EOS) is also recommended.
 
If the dose has been interrupted/restarted in 2 other instances due to ALT and/or AST results, and ALT and/or AST results are $> 3.0 \times$ ULN for a third time, study drug will be permanently discontinued, and the participant will follow EOT visit procedures; a post-treatment follow-up visit (EOS) is also recommended.
 
In parallel to the participant starting the post-treatment follow-up period, the investigator, in collaboration with the medical monitor, will determine further steps.

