6.7.4. Prohibited Medications and Procedures

The following medications and procedures are prohibited for all participants in the study:

- Conventional therapies with potential therapeutic impact on CSU, per discretion of the investigator or designee, with the exception of SOC and rescue medication.
- JAK inhibitors (systemic or topical) other than povorcitinib.
- Use of biologics with immunomodulatory effect.
- Systemic immunosuppressive or immunomodulating drugs (eg, oral or injectable corticosteroids, methotrexate, cyclosporine, dapsone, azathioprine).
- Apremilast, crisaborole, or any other systemic or topical PDE-4 inhibitor.

- Strong systemic CYP3A4 inhibitors and strong and moderate systemic CYP3A4 inducers (see [Appendix B](#)). Examples include but are not limited to the following medications: rifampicin/rifampin, ketoconazole, itraconazole, carbamazepine, ritonavir, St John's wort, and grapefruit/grapefruit juice.
 - In exceptional cases (eg, COVID-19 treatment with nirmatrelvir/ritonavir), and after study drug interruption, strong CYP3A4 inhibitors or strong/moderate inducers may be used for up to 7 days. The sponsor (or designee) must be informed of the investigator's (or designee's) decision and rationale within a reasonable timeframe. Study drug may be restarted after a minimum of 7 days of discontinuation of the strong CYP3A4 inhibitor or strong/moderate inducer.
 - If treatment with strong CYP3A4 inhibitors or strong/moderate CYP3A4 inducers is required for longer than 7 days after study drug interruption, the participant may be discontinued from the study and the ET visit performed.
- Live, attenuated vaccines (during the study and within 8 weeks after the last dose of study drug). Examples of live vaccines include but are not limited to the following:
 - BCG
 - herpes zoster
 - measles-mumps-rubella or measles-mumps-rubella-varicella
 - monovalent, live, attenuated influenza A (intranasal)
 - oral polio vaccine
 - rotavirus
 - seasonal, trivalent, live, attenuated influenza (intranasal)
 - smallpox
 - typhoid
 - varicella (chickenpox)
 - yellow fever
- Elective surgery
 - PC period: Will not be allowed
 - EXT period: May be allowed per determination of the investigator (or designee) after consultation with the sponsor (or designee). See Section [6.6.1.6](#) for details on study drug interruption.

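### Protocol 6.6.1.3 puts the 7-day limit on the study-drug interruption, where 6.7.4 puts it on the antiviral; read literally, the limit conflicts with the protocol's own 7-day washout

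*Protocol*

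**What the plan says.** Three parts of the protocol bear on this.

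- **Section 6.6.1.3 (COVID-19)** sets the interruption: "study drug must be interrupted for up to 7 days to allow the antiviral treatment course to complete". The following sentence sets the restart rule: "Study drug may be restarted after a minimum of 7 days after the last dose of the antiviral therapy".
- **Section 6.7.4 (prohibited medications)** covers the same example. It fixes the order of events ("In exceptional cases (eg, COVID-19 treatment with nirmatrelvir/ritonavir), and after study drug interruption") and limits the interacting drug: "strong CYP3A4 inhibitors or strong/moderate inducers may be used for up to 7 days". It gives the same washout: "Study drug may be restarted after a minimum of 7 days of discontinuation of the strong CYP3A4 inhibitor or strong/moderate inducer". It also allows discontinuation from the study in one case: "If treatment with strong CYP3A4 inhibitors or strong/moderate CYP3A4 inducers is required for longer than 7 days after study drug interruption".
- **Section 6.6.1 (interruptions in general)** allows up to 28 days off study drug, "unless otherwise specified in the Protocol or a longer period is approved by the sponsor (or designee), to allow for resolution of toxicity". It asks for sponsor contact about any participant "whose treatment has been interrupted for more than 21 days (but less than 28 days) before restarting treatment".

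Sections 6.6.1.3 and 6.7.4 do not refer to each other. The serious-infections row of Table 4 sends the reader to 6.6.1.3 but not to 6.7.4. Section 6.6.1 sends the reader to Appendix E for COVID-19 interruptions. Appendix E deals with visits, drug supply, monitoring and expenses, and has no antiviral dosing rule.

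**The concern.** The same figure, 7 days, limits different drugs in the two sections. In 6.6.1.3 it limits time off povorcitinib; in 6.7.4 it limits time on the inhibitor or inducer. Because the washout alone takes 7 days from the last antiviral dose, an interruption that starts before the antiviral and covers both the course and the washout will nearly always exceed 7 days.

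At stake is a dosing instruction. A site that treats the 7 days in 6.6.1.3 as a limit on the whole interruption would restart povorcitinib while the protocol still wants it withheld because of the CYP3A4 interaction. The general 28-day allowance does not settle the matter, since it gives way where the protocol specifies otherwise, and 6.6.1.3 can be read as such a case.

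**Working it through.** **Inputs.** Limit on interruption: 7 days (6.6.1.3). Minimum washout: 7 days after the last antiviral dose (6.6.1.3, 6.7.4). Maximum antiviral use: 7 days, begun after study drug is interrupted (6.7.4). Study drug is taken once daily (Section 6.1, Appendix C). The documents give no antiviral course length, so L runs from 1 to 7 days; L = 5 is an illustration only.

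**Base case.** The last study dose is on day 0 and the antiviral is taken on days 1 to L. Two counts of the washout are reasonable:

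- Restart on the 7th day after the last antiviral dose, day L + 7. Days off = (L + 7) − 1 = L + 6.
- Restart after 7 full clear days, day L + 8. Days off = (L + 8) − 1 = L + 7.

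**Variant.** Appendix C prefers morning dosing, so that day's study dose may already have been taken when the antiviral starts. Each count then falls by one, to L + 5 and L + 6.

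**Literal 7-day limit, base case.** Days 1 to 7 are off drug and restart is on day 8, which is 8 − L days after the last antiviral dose.

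| L (days) | Days off needed, base case (L+6 / L+7) | Days off needed, variant (L+5 / L+6) | Literal restart, base case: days after last antiviral dose (8−L) |
|---|---|---|---|
| 1 | 7 / 8 | 6 / 7 | 7 |
| 2 | 8 / 9 | 7 / 8 | 6 |
| 3 | 9 / 10 | 8 / 9 | 5 |
| 5 | 11 / 12 | 10 / 11 | 3 |
| 7 | 13 / 14 | 12 / 13 | 1 |

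**Can the 7-day limit be reproduced from the washout rule?** Only at the shortest courses. In the base case L = 1 fits on the first count and fails on the second, and L = 2 to 7 fails on both. In the variant L = 1 fits on both counts, L = 2 fits on the first only, and L = 3 to 7 fails on both. The conflict therefore starts at about 2 to 3 days.

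**Gap between the readings, base case.** (L + 6) − 7 = L − 1, or (L + 7) − 7 = L. That is 4 to 5 days of dosing at L = 5 and 6 to 7 days at L = 7. In the variant the literal restart is on day 9, or 9 − L days after the last antiviral dose: 4 at L = 5 and 2 at L = 7.

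**With the limit moved to the antiviral.** Earliest restart at L = 7 means 13 to 14 days off drug. That is 7 to 8 days below the 21-day contact point (21 − 14 = 7; 21 − 13 = 8) and 14 to 15 days below the 28-day limit (28 − 14 = 14; 28 − 13 = 15). The rules then agree.

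**The case against.** The strongest reply is that 6.6.1.3 says what its 7 days are for. The clause about letting the antiviral finish ties the period to the course, and the next sentence adds the washout as a second step. Section 6.7.4 gives the same sequence explicitly. The restart minimum is stated twice, so a site restarting early would have to ignore the adjacent sentence. Most of this stands: the intent is readable, and literal misuse is unlikely.

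It does not make the sentence right. As written, the 7 days governs the interruption of study drug, and the interruption does not end when the antiviral does. The reader has to repair an instruction by means of the next sentence or a section that 6.6.1.3 does not cite. If the sentence is misread, the error leads to early restart.

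The objection that the affected course lengths depend on the counting rule is also fair, which is why the threshold is given as about 2 to 3 days. Section 6.6.1.3 is a subsection of 6.6.1 and easily found, so the pointer to Appendix E is a secondary matter.

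A reader might go further and infer any of the following, which the documents do not support:

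- **That sites have no workable rule, or that following the washout breaches the protocol.** Section 6.7.4 is workable as it stands. No passage attaches a consequence to more than 7 days off study drug; the possible discontinuation in 6.7.4 depends on how long the interacting drug is needed. The discontinuation criterion in 6.6.2 concerns a persistent adverse event that interrupts drug for more than 28 days.
- **That exposure or compliance summaries are distorted.** SAP 6.4 and 6.5 subtract interrupted days in the average daily dose and compliance formulas.
- **That the primary result is affected.** SAP 7.3 uses all available UAS7 data from the placebo-controlled period, and nothing in this rule touches sample size, alpha or power.

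**Conclusion.** The point holds as a minor wording error in an operative dosing rule. Section 6.6.1.3 attaches to the study-drug interruption a limit that 6.7.4 shows belongs to the antiviral.

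The 13 to 14 days for a 7-day course assumes that study drug stops before the first antiviral dose, as 6.7.4 directs; it is 12 to 13 if that day's dose was already taken. On the base-case literal reading, povorcitinib would resume 3 days (assumed 5-day course) or 1 day (7-day course) after the last antiviral dose, where the protocol requires at least 7.

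The safety risk is small, because early restart means overlooking an explicit minimum. The documents give no number of affected participants, so no trial-level size can be stated.

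**What to change.** Replace the interruption and restart wording in 6.6.1.3 with: *Study drug must be interrupted before the first antiviral dose. The antiviral may be used for up to 7 days, and study drug may be restarted no sooner than 7 days after the last antiviral dose (see also Section 6.7.4).* Do not add a total such as 14 days. The washout is a minimum, and a stated total could be read as a new limit.

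Optionally, have 6.6.1 cite 6.6.1.3 for COVID-19 interruptions, in place of or alongside Appendix E.

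The cost is two sentences and one or two cross-references in the next amendment, or a clarification letter to sites. Design, sample size and analysis do not change. The documents do not say whether dosing is still under way; if it has finished, the correction matters only where this text is reused.

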6.6.1.4. Management of Thrombosis Events

Participants who develop symptoms of thrombosis should be promptly evaluated and treated appropriately.

The participant must be discontinued from study drug if the diagnosis of the following is confirmed: venous thrombosis (such as but not limited to deep vein thrombosis and pulmonary embolism), arterial thrombosis (such as but not limited to MI and stroke), or any other thromboembolic event.

6.6.1.5. Management of Malignancy

Participants who develop malignancy other than nonmelanoma skin cancer or carcinoma in situ of the cervix must be discontinued from study drug. Information including histopathological results should be queried for the confirmation of the diagnosis.

Periodic skin examination is recommended for participants who are at increased risk for skin cancer.

6.6.1.6. Emergency and Elective Surgeries

If a participant must undergo emergency surgery, the study drug should be interrupted at the time of the surgery. After emergency surgery, allow reintroduction of study drug once the physician has examined the surgical site and determined that it has healed and there is no sign of infection.

Elective surgery, and interruption of study drug for such a surgery, may be allowed during the EXT period. If the participant undergoes elective surgery, the study drug should be interrupted at least 1 week prior to the planned surgery. Allow reintroduction of study drug once the physician has examined the surgical site and determined that it has healed and there is no sign of infection.

6.6.2. Criteria for Permanent Discontinuation of Study Drug

The occurrence of unacceptable toxicity not caused by the underlying disease will require that the study drug be permanently discontinued. Unacceptable toxicity is defined as follows:

- The occurrence of an AE that is related to study drug that, in the judgment of the investigator or the sponsor's medical monitor, compromises the participant's ability to continue study-specific procedures or is considered to not be in the participant's best interest.
- A persistent AE requiring an interruption of study drug for more than 28 days unless a greater delay has been approved by the sponsor (or designee).
- Recurrence of an initial AE(s) that previously led to study drug interruption after restarting the study drug (unless otherwise specified in [Table 8](#)).
- Specific AEs requiring permanent discontinuation of study drug as described in [Section 6.6.1](#).

See [Section 7](#) for discontinuation procedures.

6.7. Prior and Concomitant Medications and Procedures

6.7.1. Prior Therapy for Chronic Spontaneous Urticaria

Any topical or systemic treatments for CSU since initial diagnosis will be recorded in the eCRF. Information associated with response to prior CSU therapy and reason for discontinuation will also be recorded in the eCRF. Examples of commonly used therapies for CSU include but are not limited to the following: second-generation H1 antihistamines, omalizumab, corticosteroids, and cyclosporin.

6.7.2. Background (Standard of Care) Therapy

All participants will be required to remain on a concurrent, stable dose of second-generation H1 antihistamine as background therapy (SOC), which will not be changed throughout the study. Choice of SOC regimen will be left to investigator discretion.

6.7.3. Rescue Medication

Initiation of non-study drug therapy to treat the worsening of pruritus, CSU, or flare of previously inactive skin disease is strongly discouraged throughout the PC period. If deemed to be medically necessary by the investigator, rescue treatments for CSU noted below may be added to study drug and background therapy.

All rescue medication must be entered into the EDC and classified as rescue medication with the following information:

- Name and dose regimen of the rescue medication.
- Date and time of administration.

From Week 1 to Week 4:

- Add another second-generation H1 antihistamine to treatment regimen.

From Week 5 to Week 36:

- Add another second-generation H1 antihistamine to treatment regimen.
- In the case of severe exacerbation of pruritus, a 1-time, short course (maximum 7 days) of glucocorticosteroids may be used as rescue medication from Day 1 of Week 5.
- If rescue medication is to be added, the efficacy and safety assessments for the visit should be completed before the start of rescue therapy.
- The participant may remain on study drug unless the rescue therapy is a prohibited medication or procedure.

From Week 36 to Week 44 (Post-Treatment Follow-Up Period):

- Any participant experiencing a worsening of symptoms can be treated with any rescue therapy deemed appropriate by the investigator.

6.7.4. Prohibited Medications and Procedures

The following medications and procedures are prohibited for all participants in the study:

- Conventional therapies with potential therapeutic impact on CSU, per discretion of the investigator or designee, with the exception of SOC and rescue medication.
- JAK inhibitors (systemic or topical) other than povorcitinib.
- Use of biologics with immunomodulatory effect.
- Systemic immunosuppressive or immunomodulating drugs (eg, oral or injectable corticosteroids, methotrexate, cyclosporine, dapsone, azathioprine).
- Apremilast, crisaborole, or any other systemic or topical PDE-4 inhibitor.

- Strong systemic CYP3A4 inhibitors and strong and moderate systemic CYP3A4 inducers (see [Appendix B](#)). Examples include but are not limited to the following medications: rifampicin/rifampin, ketoconazole, itraconazole, carbamazepine, ritonavir, St John's wort, and grapefruit/grapefruit juice.
 - In exceptional cases (eg, COVID-19 treatment with nirmatrelvir/ritonavir), and after study drug interruption, strong CYP3A4 inhibitors or strong/moderate inducers may be used for up to 7 days. The sponsor (or designee) must be informed of the investigator's (or designee's) decision and rationale within a reasonable timeframe. Study drug may be restarted after a minimum of 7 days of discontinuation of the strong CYP3A4 inhibitor or strong/moderate inducer.
 - If treatment with strong CYP3A4 inhibitors or strong/moderate CYP3A4 inducers is required for longer than 7 days after study drug interruption, the participant may be discontinued from the study and the ET visit performed.
- Live, attenuated vaccines (during the study and within 8 weeks after the last dose of study drug). Examples of live vaccines include but are not limited to the following:
 - BCG
 - herpes zoster
 - measles-mumps-rubella or measles-mumps-rubella-varicella
 - monovalent, live, attenuated influenza A (intranasal)
 - oral polio vaccine
 - rotavirus
 - seasonal, trivalent, live, attenuated influenza (intranasal)
 - smallpox
 - typhoid
 - varicella (chickenpox)
 - yellow fever
- Elective surgery
 - PC period: Will not be allowed
 - EXT period: May be allowed per determination of the investigator (or designee) after consultation with the sponsor (or designee). See Section [6.6.1.6](#) for details on study drug interruption.

Note: If a participant must undergo emergency surgery, the study drug should be interrupted at the time of the surgery. See Section [6.6.1.6](#) for details on study drug interruption.

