7. DISCONTINUATION OF STUDY TREATMENT AND PARTICIPANT WITHDRAWAL

7.1. Discontinuation of Study Treatment

7.1.1. Reasons for Discontinuation

Participants **must** be discontinued from study treatment for the following reasons:

- The participant becomes pregnant.
- Consent is withdrawn.

Note: Consent withdrawn means that the participant has explicitly indicated that they do not want to be followed any longer; in this case no further data, except data in the public domain, may be solicited from or collected on the participant. Consent may also be partial. Participants may choose to discontinue study drug and remain in the study to complete the post-treatment follow-up visit.

- Further participation would be injurious to the participant's health or well-being, in the investigator's medical judgment.
- Occurrence of unacceptable toxicity as noted in Section 6.6.
- Has received a prohibited medication or procedure as described in Section 6.7.4.
- The study is terminated by the sponsor.
- The study is terminated by the local health authority, IRB, or IEC.

A participant **may** be discontinued from study treatment as follows:

- If a participant is consistently noncompliant with study procedures or with study drug or background therapy administration in the investigator's opinion, the sponsor should be consulted for instruction on handling the participant.

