8.7. End of Treatment and Early Termination

The EOT1 (PC period) coincides with the Week 12 visit, and the EOT2 (EXT period) coincides with the Week 36 visit. A participant who completes the Week 12/EOT1 visit will have completed the PC period and may continue into the EXT period. A participant who completes the Week 36/EOT2 visit will have completed the EXT period.

If a decision is made that the participant will permanently discontinue study drug prior to the Week 36/EOT2 visit, then the ET visit should be conducted and will be determined as ET1 (if during the PC period) or ET2 (if during the EXT period). If the ET visit coincides with a regular study visit, then the ET evaluations will supersede those of that scheduled visit, and the data should be entered in the ET visit in the eCRF. If this decision does not coincide with a regular visit, reasonable efforts should be made to have the participant return to the site to complete the ET procedures. The participant should be encouraged to return for the follow-up visit.

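### The corticosteroid ban in Protocol Section 6.7.4 does not exempt the steroid rescue course that Section 6.7.3 allows, so read literally an allowed oral or injected course forces study drug to stop

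*Protocol*

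**What the plan says.** **The permission.** Protocol Section 6.7.3 states that, for severe exacerbation of itch, "a 1-time, short course (maximum 7 days) of glucocorticosteroids may be used as rescue medication from Day 1 of Week 5". No route is given. Its opening paragraph says that "rescue treatments for CSU noted below may be added to study drug and background therapy", so the course is meant to be given with study drug continuing. The list for Weeks 5 to 36 then ends with a condition: "The participant may remain on study drug unless the rescue therapy is a prohibited medication or procedure".

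**The ban.** Section 6.7.4 applies to all participants. One bullet prohibits "Systemic immunosuppressive or immunomodulating drugs (eg, oral or injectable corticosteroids, methotrexate, cyclosporine, dapsone, azathioprine". That bullet has no exception for rescue, duration or study week. The only mention of rescue in the section is in a different bullet, which prohibits "Conventional therapies with potential therapeutic impact on CSU, per discretion of the investigator or designee, with the exception of SOC and rescue medication".

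**The consequence.** Section 7.1.1 lists the reasons for which study treatment must be stopped. One of them is: "Has received a prohibited medication or procedure as described in Section 6.7.4".

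**The estimand.** Protocol Table 16 and SAP Table 5 list use of protocol-allowed rescue as an intercurrent event separate from treatment discontinuation. Both events are handled by treatment policy.

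**The concern.** Three sections have to be read together to decide what happens after a steroid rescue course, and they do not agree. Section 6.7.3 adds the course to study drug. Sections 6.7.4 and 7.1.1, taken as written, require study drug to stop once the steroid is oral or injected. Sites could therefore handle the same event differently, and a monitor could hold a site to the mandatory rule.

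The stake for the analysis is the Week 12 UAS7, which comes only from the daily diary. If study drug is stopped before Week 12, the participant moves to an early-termination visit and the diary may end there. The estimand intends to use the Week 12 value regardless of rescue, so the value could be lost precisely where the plan says it should be kept. In the responder analyses (SAP Section 7.4.1), a participant with no Week 12 response on record counts as a nonresponder.

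**Working it through.** This is mainly a textual check. Each step asks whether some provision breaks the chain from allowed rescue to mandatory discontinuation.

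1. **Does the ban reach the rescue course?** Section 6.7.3 gives no route, and the Section 6.7.4 bullet names oral and injected corticosteroids. A topical course falls outside that bullet; an oral or injected one falls inside it. The point is limited to the latter. That a short course for a severe flare would usually be systemic is plausible, but it is an assumption.

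2. **Does the rescue exemption in Section 6.7.4 cover it?** The exemption belongs to the conventional-therapies bullet. Section 6.7.1 supports treating steroids as conventional CSU therapy: "Examples of commonly used therapies for CSU include but are not limited to the following: second-generation H1 antihistamines, omalizumab, corticosteroids, and cyclosporin". But the bullets are separate prohibitions, and exemption from one does not lift another. Elsewhere the section places an exception inside the bullet it modifies: povorcitinib itself in the JAK-inhibitor bullet, up to 7 days of use for CYP3A4 agents, and elective surgery in the extension. Exclusion criterion 11e (Section 5.2) likewise carries its own corticosteroid notes. A reader could fairly infer that a bullet with no exception has none.

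3. **Does Section 6.7.3 settle it?** No. Its closing condition makes staying on study drug depend on the rescue not being prohibited, which sends the reader back to Section 6.7.4.

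4. **Does Section 7.1.1 exempt rescue?** No. It refers to Section 6.7.4 as a whole.

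The literal chain is therefore closed.

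5. **What follows for the data?** Section 8.7 says that if the participant will "permanently discontinue study drug prior to the Week 36/EOT2 visit, then the ET visit should be conducted"; in the placebo-controlled period this is ET1. Table 3 schedules the diary daily to Week 44, or to early termination where that applies. Section 7.1.2 lets participants who stop treatment continue in follow-up, efficacy assessments included, but it does not set a Week 12 assessment for them. The MMRM (Protocol Section 10.4.1, SAP Section 7.3) does not impute missing values.

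**Arithmetic, from the documents only**

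| Quantity | Inputs | Result |
|---|---|---|
| Placebo-controlled weeks in which the conflict is live | Weeks 5 to 12: 12 − 4 | 8 of 12 (67%) |
| Treatment weeks in which it is live | Weeks 5 to 36: 36 − 4 | 32 of 36 (89%) |
| Postbaseline placebo-controlled visits it can affect | Weeks 8 and 12, out of Weeks 4, 8 and 12 (Table 3) | 2 of 3 |
| Weight of one missing Week 12 value | 1 / 34 planned per arm (Protocol Section 10.1) | 2.9% |

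These figures describe where the conflict can act. They do not measure its effect. The documents give no steroid-rescue rate and no basis for how many sites would read the ban literally.

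**The case against.** The best reply is that nobody would be misled. The course is allowed in Protocol Sections 1, 2.2.1, 4.1 and 6.7.3 and again in SAP Section 3. Section 2.2.1 uses rescue to justify the placebo arm. The estimand names protocol-allowed rescue separately from discontinuation, and SAP Appendix A plans Table 2.3.13.1 on corticosteroid treatment of CSU up to Week 36. A specific, repeated permission should override a general bullet, and the closing condition in Section 6.7.3 is more naturally read as covering rescue that the section does not list. This stands as evidence of intent. It does not tell a site or monitor which rule governs when one of the rules is mandatory.

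Second, the harm needs a run of events: a steroid course, a literal reading, study drug stopped, the diary ended, and no continuation under Section 7.1.2. No step has a known probability, and Week 4 and any Week 8 values already collected still enter the MMRM. This is correct, and it is why no count or bias is claimed.

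Third, the loss of diary data at early termination arises after any permanent discontinuation, whatever its cause. That is also true. What is specific here is that the text can create a discontinuation the plan did not intend.

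Fourth, Section 7.1.2 requires the monitor or sponsor to be told of each discontinuation, so a misreading could be noticed, and site manuals not available here may already clarify the point. Notification comes with the decision to stop, however, and instructions that cannot be seen cannot be relied on.

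**Conclusion.** The concern holds. For an oral or injected course, Sections 6.7.3, 6.7.4 and 7.1.1 give conflicting instructions, and the literal result (stopping study drug after allowed rescue) is not what the plan intends. Confidence in the textual conflict is high.

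The effect on the primary endpoint is possible rather than shown. It depends on a site reading the ban literally and on the participant's diary ending before Week 12. The number affected and the direction of any bias cannot be determined from the documents. The point should be corrected because it concerns a mandatory stopping rule, can cost primary-endpoint data and is easily removed. It does not call the design or the analysis into question.

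**What to change.** In Protocol Section 6.7.4, add to the systemic immunosuppressant bullet: *except the one-time glucocorticosteroid rescue course permitted in Section 6.7.3*. Section 7.1.1 and the closing condition in Section 6.7.3 both work by reference to what is prohibited, so they follow without further edits.

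Tell sites that:

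- allowed rescue is not in itself a reason to discontinue study drug;
- the participant may stay on study drug at the investigator's judgment;
- the daily diary should continue.

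The cost is one phrase and a site communication, handled as a minor amendment or a clarification letter. If it goes through as an amendment, the approval steps in Protocol Section 11.1 may apply. The estimand, analysis and sample size do not change.
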